This bar chart presents a comparative examination of the rates of stone expulsion for patients who were suggested to take Tamsulosin or Silodosin during three distinct time periods—less than 14 days, 14–21 days, and 21–28 days.

The results are color-coded, with red bars denoting silodosin and blue bars denoting tamsulosin.

Silodosin shows a markedly greater efficacy in stone expulsion, with about 55 patients expulsing stone in less than 14 days in comparison to just about 5 patients on Tamsulosin.

This suggests that Silodosin is far more successful at facilitating stone removal in less time than Tamsulosin.

While in 14–21days duration, Silodosin continues to work better than Tamsulosin in removing stones. About 20 patients on Tamsulosin were able to successfully remove stone, compared to about 30 people on Silodosin. This implies that while tamsulosin is also beneficial, silodosin retains greater efficacy.

In the span of 21–28 days, 57 patients on Tamsulosin while 13 on Silodosin were able to eliminate stones. In general, Silodosin is quite successful for rapid stone ejection during the first two weeks. Using the intended period for stone

ejection to guide medicine selection, this time-dependent efficacy analysis offers clinicians important information.

[figure not shown]

Figure 3 Survival function

This statistical method is commonly used to estimate the time until an event occurs and to compare the survival curves of different groups. In this case, Kaplan–Meier analysis was performed to assess the duration that patients required to expel kidney stones while receiving either silodosin or tamsulosin treatment. The rate of the expulsion of stone and the time for it, for both groups, was evaluated using this method, as can be seen in Figure 2.

The log-rank test was applied to compare the rate and time for stone expulsion between the two groups. It is a hypothesis test for comparing the survival distributions of two samples. It was used in this study to see if patients treated with silodosin and those treated with tamsulosin had significantly different times for stones to be expelled. With a p-value of 0.05, the log-rank test findings showed that there was statistically significant difference between the two groups. This indicates that both groups' times to stone expulsion were statistically comparable.

The data showed that patients treated with silodosin demonstrated a higher rate of stone expulsion and faster stone expulsion compared to those treated with Tamsulosin. Though the difference did not achieve statistical significance in this trial, it shows that silodosin may be more beneficial in aiding kidney stone removal. The evaluation of rate and time of stone expulsion for both groups was conducted using Kaplan–Meier analysis, as depicted in Figure 2. This statistical method is commonly used to estimate the time until an event occurs and to compare the survival curves of different groups. In this context, the Kaplan–Meier analysis was utilized to assess the duration it took for patients to expel kidney stones while being treated with either silodosin or tamsulosin.

DISCUSSION

After prostate pathology and urinary tract infections, renal stones are the third most frequent urinary tract disorder. Ureteral stones account for 14% of stones in the urinary system, most of which are in the distal ureter. Five to ten percent of people have urolithiasis. Their rising incidence is a serious cause for concern(35).

Stones can be treated medically or surgically according to European and American urology associations. The medical management (MET) has its own advantages and is preferred over surgical approach as it is has less risks involved than the surgical procedures. For (MET) medical expulsive therapy we need to keep in view various parameters including the stone's size, position, and ureteric characteristics. The medical care of ureteral calculi has significantly improved since the market saw the release of efficient medicinal therapeutic agents. The results of multiple investigations suggest that alpha blockers aid in the transit of ureteral stones. These have shown that this strategy may speed up and ease the ureteral stones' natural passage. α -AR blockers have been suggested by recent worldwide standard guidelines as a treatment for ureteral stones in adults and adolescents.

In 1970, it was initially reported on how adrenergic receptors function in the human ureter. Alph adrenergic receptor agonists preserve ureteral peristalsis, which may aid in a spontaneous stone passage, while also preventing the uncoordinated muscular activity associated with renal colic. Instead of totally stopping the action of the ureteric smooth muscle, alpha blockers primarily cause relaxation of the human ureter's distal portion.

There are three different types of alpha receptors. α 1A-receptor α -1B, and α 1D. Older alpha blockers had interactions with all subtypes of alpha receptors and therefore had more incidence of adverse effects like postural hypotension and retrograde ejaculation etc.

Tamsulosin is highly selective for α 1A and α 1D receptors and has lesser incidence of side effects like postural hypotension, retrograde ejaculation, headache and gastritis as compared to aforementioned drugs with receptor non selectivity () Silodosin is a selective alpha 1 blocker and is also used recently as medical expulsive therapy.

After being approved in Japan in 2006, the recently introduced selective α -1A AR antagonist silodosin is currently licensed in over 50 countries, including the US and Europe, for the treatment of lower urinary tract symptoms (LUTS).

Given the growing body of evidence supporting the efficacy of medical expulsive therapy (MET) with selective α -blockers, MET treatment for ureteral stones is a financially prudent approach (36).

In our study, we wanted to compare the efficacy of two drugs in MET (medical expulsive therapy) with regards to stone expulsion rate as well as to compare the side effect profile in our population.

Patients with distal ureteral calculi who received alpha blocker drugs had almost 40-50% higher chances of expulsion of stone than those who did not receive this treatment, according to two meta-analyses that offered strong evidence for the clinical benefit of this treatment [29, 34]. Hollingsworth and colleagues recently conducted a meta analysis of trials utilizing alpha blockers in individuals with ureteral stones, and they obtained similar results.

According to a study, an alpha-1A receptor antagonist may not be as helpful for stone ejection as a specialized α -1D receptor antagonist.

According to a different study, using α -1A adrenoceptor blockers instead of α -1D adrenoceptor blockers can result in more successful stone expulsions. Tamsulosin and silodosin exhibit comparable α -1D receptor subtype affinity when taken at a dose of 8 mg once day. However, silodosin has about 38 times greater affinity for α -1A receptors than tamsulosin does(37). Approximately 95% of stones with a diameter of less than 4 mm passed after 40 days of conservative treatment alone, according to a research. On the other hand, silodosin exhibited a greater stone expulsion rate of 14% in comparison to tamsulosin for larger stones, measuring 5-10 mm in diameter. For distal ureteral stones treated with silodosin, the mean ET (in days) ranged from 6.5 to 16.7 days. Those with symptomatic unilateral ureteral calculi less than 10 mm in diameter were assigned to receive silodosin (8 mg/day) and instructed to consume two liters of water per day for a maximum of eight weeks in a prospective randomized research. The average ET was 10.27 ± 8.35 days overall. The mean ET for distal ureteral stones was 9.29 ± 5.91 days. The mean ET was 9.56 ± 8.45 days for stones with a diameter of 1–5 mm and 11.33 ± 8.31 days for stones with a diameter of less than 10 mm(38).

Our study showed the that 51.9% of the patients with proximal ureteric stone were given Tamsulosin and 48.1% received Silodosin. 82.6 percent of patients with mid-ureteric stone problems received Silodosin, while 17.4% received Tamsulosin. While 51.9% of patients with distal ureteric stones received Tamsulosin and 48.1% Silodosin.

Numerous meta-analyses have investigated how different medication combinations affect ureteric stone treatment. However, there aren't many studies that specifically compare how well different alpha-blockers work to cure distal ureteric calculi. For distal ureteric stones, the use of supplementary drugs such Tamsulosin has been shown to be beneficial in easing discomfort, lowering risks, and quickening the removal of the stone. According to recent studies, silodosin might be a suitable and effective replacement(39).

In treating distal ureteral calculi silodosin performed better than a placebo or tamsulosin, per a recent meta-analysis. However Silodosin's safety profile was comparable to that of tamsulosin (40).

In another study involving 167 paediatric patients with distal ureteric stones (DUS) less than 1 cm were enrolled in this prospective single-blind placebocontrolled randomized research. The patients were randomly assigned to three groups: 1st group was given 4 mg of Silodosin once a day, 2nd group was given 0.4 mg of Tamsulosin, and 3rd group received neither medication. For a maximum of four weeks, the study groups' adverse medication reactions, the frequency and duration of expulsion of stone, an pain episodes frequency were compared. In groups I, II, and III, the rates of stone expulsion were 89.3% (50 out of 56 patients), 74.5% (41 out of 55 patients), and 51.8% (29 out of 56 patients), respectively. Group I had a significantly greater stone expulsion rate than groups II and III (p = 0.04 and p < 0.001, respectively). The stone ejection rate was higher in group II than in group III, with a statistically significant difference (p = 0.01). In groups I, II, and III, the corresponding expulsion times in days were 12.4 ± 2.3 , 16.2 ± 4.2 , and 21.2 ± 5.6 . Group I experienced a considerably shorter time to expulsion compared to groups II and III (p < 0.001). Additionally, Table 2 shows that group II's expulsion time was much lower than group III's (p < 0.001). There was no significant difference between groups I and II (p = 0.8), although group I and II had considerably fewer mean daily pain episodes requiring analgesia than group III (p < 0.001).

The size, location, and makeup of the stone, the degree of the blockage, and the symptoms all influence the best course of action. The therapy of ureteral stones has undergone a paradigm change in the last ten years due to the advent of less intrusive techniques and the availability of more advanced pharmaceutical agents.(32)

Comparably, silodosin demonstrated a statistically significant greater efficacy in terms of stone ejection rate and time compared to tamsulosin (82.4 vs. 61.5%) in another study involving adult patients.(41). Along with pain episodes and safety outcomes like orthostatic hypotension and retrograde ejaculation, the key outcomes that were taken into consideration were the stone expulsion rate (SER) and stone expulsion time (SET).

For patients with ureteral stones (distal ureteral stones with a diameter of \geq 5 mm and \leq 10 mm), silodosin is very efficient in promoting stone expulsion with shorter expulsion times and fewer pain episodes. Additionally, it works well after lithotripsy to speed up stone movement and emphasize clearance rate(37). Dell'Atti L. evaluated the effectiveness of Tamsulosin and Silodosin in the ejection of 4–10 mm ureteral stones in distal parts of urethra. The research included 136 patients in total, all of whom were at least 18 years old. For three weeks, group 1 (67 patients) got 0.4 mg of tamsulosin daily, while group 2 (66 patients) received 8 mg of silodosin daily. Compared to Tamsulosin (61.2%, 41 out of 67 patients), patients treated with Silodosin experienced a statistically significant increase in the expulsion rate (80.3%, 53 out of 66); Silodosin also demonstrated a statistically significant advantage in terms of stone expulsion rate (p: 0.003) and expulsion time (weeks) (p: 0.002). There were no reported serious problems(42).

The rate and time of stone expulsion for both groups was evaluated using this method, as can be seen in Figure 2.

One main result of our study was 89.7% of patients on silodosin had their stone removed in less than 14 days, while only 10.3% of the patients on Tamsulosin had their stone removed in aforementioned duration. Also, 72.5% of patients on Silodosin had their stone removed in 14-21 days, while only 27.5% of the patients on Tamsulosin had their stone removed in same duration. Moreover, 81.4% on Tamsulosin had their stone removed in 22-28 days and 18.6% patients on Silodosin had it removed in same duration.

A similar meta analysis matched our results. Every study that was part of the analysis prescribed silodosin for at least two weeks. The results of several researches were compared by observing the effects of silodosin over a standardized period of time thanks to this constant timeframe. The results of this investigation showed that individuals with distal ureteral stones saw significantly higher rates of stone ejection when they received Silodosin for at least two weeks. This implies that silodosin worked well to help stones transit through the body in a short amount of time, which may lessen the need for more intrusive procedures and enhance patient outcomes when treating distal ureteral stones(43).

A meta-analysis was carried out on the similar comparison and it showed that mean stone ejection time was shorter in patients receiving silodosin 8 mg daily compared to those directed to drink 2 L of water daily and a greater rate of stone ejection. Meta-analyses conducted since the silodosin RCT have demonstrated that efficacy of silodosin is more than that of tamsulosin for the Medical expulsive therapy of ureteral stones. The meta analyses discovered that silodosin, as opposed to tamsulosin, dramatically raised the expulsion rate of distal ureteral stones in a meta-analysis involving five RCTs(44).

A positive but weak link was seen when the length of stone ejection was analyzed in relation to the frequency of renal colic episodes, the dosage of analgesics, and the size of the stone (Table 4; P<0.001). The number of renal colic episodes and the dose of analgesics were found to be positively and strongly correlated (P<0.001), the number of renal colic episodes and stone size was found to be positively and weakly correlated (P=0.015), and the analgesic dosage and stone size was found to be positively and to be positively and weakly correlated (P<0.05)(28).

Overall, compared to 30% of patients in the placebo group, 37.5% of patients in the tamsulosin group experienced drug-related side events (p = 0.7). The most often reported side effect was dizziness, which was more common with tamsulosin (25%) than with placebo (22.5%) (p = 0.9). Other adverse effects (sinus pressure, nosebleed, nausea, tinnitus, hands and feet swelling) that may or may not be related to the medication were recorded in isolated cases. In neither group were there any significant side effects noted. However, men in the tamsulosin group experienced ejaculatory dysfunction more frequently [5 (17.9%) vs. 1 (3.5%), (p = 0.1)].

Because both medications are safe and well tolerated, no significant side effects were seen in the trial. In groups A and C, anejaculation was experienced by 17 out of 23 patients (73.9%) and 21 out of 25 patients (84%) respectively; nevertheless, none of the patients stopped receiving treatment. After the treatment was discontinued, the situation rapidly improved. In the study patients, there was no significant change in their blood pressure or pulse rate. A study of the literature supports the findings, showing no correlation between changes in blood pressure or heart rate and a 50 mg dose of mirabegron(45).

Our Patients on tamsulosin accounted for 40.1% of those who did not report any side effects; those on silodosin made for a larger percentage (59.9%). This implies that, in comparison to Tamsulosin, Silodosin may have a marginally higher correlation with patients reporting no adverse effects.

There was no discernible difference in the reported orthostatic hypotension values of 3.6, 5.5, and 1.8% for the silodosin, tamsulosin, and placebo groups, respectively. Other side effects were noted in the silodosin, tamsulosin, and placebo groups, respectively, and included headache (3.6, 5.5, and 1.8%), dizziness (7.1, 10.9, and 3.6%), nasal congestion (1.8, 3.6, and 0), and nausea (1.8, 3.6, and 1.8%), all without a statistically significant difference. Based on the Common Terminology Criteria for Adverse Events, version 4.0, all cases were rated as grade 1(46).

The groups who took silodosin alone and the group that took silodosin plus tadalafil experienced similar side symptoms, such as headache, dizziness, backache, orthostatic hypotension, and retrograde ejaculation (Table-III). Given that P > 0.05, that was not statistically significant(41).

Examining particular side effects reveals various themes. Nine patients on tamsulosin (60.0%) and six patients on silodosin (40.0%) developed orthostatic hypotension, a condition marked by a considerable drop in blood pressure upon standing. Despite the fact that the sample size for this particular side effect is rather modest, it suggests that Tamsulosin users are more likely to have orthostatic hypotension than Silodosin users.

According to a study, the most common adverse event associated with the silodosin group was decreased or absent ejaculation. Of the patients in groups A and B, eight patients (8 were distressed, four were not, and six were distressed but could wait for their improvement) and nineteen patients (10 were distressed, four were not, and five were distressed but could wait for their improvement) experienced this adverse event most frequently(47).

Only a very tiny percentage of patients reported experiencing abnormal ejaculation; 2 individuals on tamsulosin (66.7%) and 1 patient on silodosin (33.3%) reported this side event. Again, this points to an increased chance of this specific adverse effect in Tamsulosin users, but the numbers are too low to make any firm conclusions. Another side effect that was identified involved headaches, which were seen by 4 individuals on silodosin (44.4%) and 5 patients on tamsulosin (55.6%). Headaches were marginally more common among Tamsulosin users compared to Silodosin users, similar to orthostatic hypotension.

Many urologists agree when it comes to the incidence of retrograde ejaculation that it is an indication of therapy efficacy rather than a negative effect. It seems that silodosin relaxes the smooth muscles in the genital and lower urinary tracts sufficiently to cause a retrograde ejaculation. Retrograde ejaculation was more common in the individuals who experienced the most alleviation from lower urinary tract symptoms, which was consistent with this conclusion. This finding implies that the retrograde ejaculation is, in fact, a passive marker of the smooth muscle relaxation brought on by silodosin(32).

Typically, nonselective $\alpha 1$ adrenoceptor antagonists such doxazosin and terazosin are linked to orthostatic hypotension. Nonetheless, in clinical trials, silodosin was linked to a modest incidence of orthostatic hypotension. According to the combined analysis of the US and European studies, 1.1% of patients receiving a placebo and 1.3% of patients receiving silodosin experienced orthostatic hypotension(48).

When compared to Tamsulosin, Silodosin is linked to a larger incidence of retrograde ejaculation but a reduced incidence of peripheral vasodilation-related adverse effects, such as orthostatic hypotension and dizziness, according to a retrospective review conducted by Imperatore et al(49).

In our study comparing the effects of Tamsulosin and Silodosin on patients, it was discovered that only 38.1% of those receiving Silodosin needed analgesics to ameliorate ureteric pain. On the other hand, 61.9% of patients receiving Tamsulosin required analgesic intervention, which is a far larger percentage. This significant difference raises the possibility that silodosin is more successful in treating ureteric stones and it also lowers their need for extra painkillers.

Similar results were seen in another study showing that, individuals receiving just tamsulosin treatment needed a greater average analgesic dosage of 391.43 \pm 165.60 mg with a p-value of 0.005, which denotes substantial significance, the necessary(50).

Similarly, a study showed statistically significant difference in the amount of analgesics needed by patients treated with Silodosin compared to those treated with tamsulosin only. The robustness of the conclusion was highlighted by the fact that the group receiving Silodosin treatment required considerably fewer analgesics than the groups receiving Tamsulosin, with a p-value of < 0.001(51).

Conclusion

An effective treatment for ureteral stones is medical expulsive therapy. According to our findings, silodosin has a safer profile and is more successful than tamsulosin at ejecting ureteric stones.

Silodosin had an increased rate of stone expulsion and took less time in stone expulsion compared to those treated with Tamsulosin.

In addition, patients treated with silodosin reported fewer side effects, such as a retrograde ejaculation, orthostatic hypotension and headaches as compared to those taking Tamsulosin.

In addition, those who received Silodosin needed less analgesic medication than those who received Tamsulosin.

•

REFERENCES

- Ahmed AFAM, Al-Sayed AYS. Tamsulosin versus Alfuzosin in the Treatment of Patients with Distal Ureteral Stones: Prospective, Randomized, Comparative Study. Korean J Urol. 2010 Mar;51(3):193–7.
- 5. Pietropaolo A, Proietti S, Geraghty R, Skolarikos A, Papatsoris A, Liatsikos E, et al. Trends of 'urolithiasis: interventions, simulation, and

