Table 2	Association between Tamsulosin and	35
	Silodosin with side effects	

LIST OF FIGURES

Serial No.	Figure	Page No
Figure 1:	Pie chart of patients using Silodosin and Tamsulosin (Medicine Advised)	33
Figure 2	Bar Chart showing comparison of stone expulsion rate in Tamsulosin and Silodosin groups	43
Figure 3	Survival function	41

L	

LIST OF ABBREVIATIONS

AUA	American Urology Association
EAU	European Association of Urology
MET	Medical expulsive therapy
PNL	Percutaneous Nephrolithotomy
RCTs	Randomized controlled clinical trials
SPSS	Statistical Package for the Social Sciences
α-AR	Alpha adrenergic receptor
LUTS	Lower Urinary Tract Symptoms

SWL	Shock wave lithotripsy
ESWL	Extracorporeal Shock Wave Lithotripsy
CKD	Chronic kidney disease
SET	Stone ejection time
USD	Ureteric stone disease
SER	Stone ejection rate

Abstract

Introduction: Ureteric stones is a very common disease world over. Medical Expulsive therapy (MET) for stones is a recognized treatment option practiced. Tamsulosin is used commonly in our population for MET however Silodosin another highly uroselective newer drug, with lesser side effects, is not used frequently for this purpose and is still under research. Both of these drugs lead to relaxation of lower ureteric smooth muscle hence facilitate in stone removal.

The rationale of this study is to compare the efficacy of Tamsulosin and Silodosin in MET (medical expulsive therapy) with regards to stone expulsion rate as well as to compare the side effect profile in our population.

Methodology: This is a prospective randomized control trial in Outpatient department of Sir Ganga Ram hospital, Lahore, on 208 patients with ureteric stone who fulfil the inclusion criterion, divided randomly into two groups with 104 patients in the Tamsulosin group and 104 patients in Silodosin group (1:1 ratio). However, 16 patients were subsequently excluded on account of premature end of study, and 12 due to being lost to follow-up (Figure 1). Out of remaining 180 patients 89 were of Tamsulosin and 93 were in Silodosin group. Demographic data including patients' age and comorbid, stone-related data including size, location, laterality and number of stones and duration of symptoms were recorded. The patients were called for follow up at 4 weeks

with an X-ray KUB without bowel preparation. We noted if the stone had passed or not.

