Data will be entered and analyzed on SPSS version 22. Percentages and frequencies will be calculated for the demographic variables of the patients. The comparison of the two groups will be made by using T- test. P-value of less than 0.05 will be considered significant and the power used will be 0.80.

RESULTS

Frequency and percentage of demographic data

Variables		Frequency	Percentage	
Gender	Male	105	58.7	
	Female	74	41.3	
Income	Less than	108	60.3	
status	50000			
	50000 -150000	69	38.5	
	Greater than	2	1.1	
	150000			
	Normal	166	92.7	
BMI	Obese	13	7.3	
	None	136	76.0	
Comorbidity	HTN	33	18.4	
	Diabetes	10	5.6	

This information sheds light on the sample population's health and demographic distribution, showing a preponderance of people with normal BMIs and lower income levels, as well as a significant percentage of people without comorbid diseases.

In our study there are total 179 patients out of which 74 are females (41.3%) and 105 males (58.7%).

The income, 108 people, or 60.3% of the total, make less than 50,000Rs in month. Just 2 members, or 1.1 percent, make more than 150,000 monthly, while 69 participants (38.5%) have monthly salaries between 50,000 and 150,000.

13 persons (7.3%) are classed as obese, while 166 people (92.7%) have a normal BMI. These numbers represent a sizable fraction of the sample. In terms of comorbidities, 136 individuals (76.0%) state they have no comorbid conditions. Of the people with comorbidities, 10 (5.6%) had diabetes, and 33 (18.4%) had hypertension (HTN).

[figure not shown]

Figure 1: Pie chart of patients using Silodosin and Tamsulosin (Medicine Advised)

Use of medicine (Figure 1)

Tamsulosin and Silodosin, the two drugs prescribed to a group of patients, are distributed as shown in the pie chart. Of the patients, 43% were advised to take Tamsulosin, which is shown as the blue section on the chart. And (57%) of the patients were advised to take silodosin, as shown by the red segment.

Table2: Patient demographic characteristics and study variables are

Varibales	Tamsulosin	Silodosin	p-value	
Body Mass index	Normal	72(43.4%)	94(56.6%)	0.730
	obese	5 (38.5%)	08(61.5%)	
Laterality	Right	65(55.6%)	52(44.4%)	0.001
	Left	12(19.4%)	50(80.6%)	
Symp To CT	Less than 1 week	67(64.4%)	37(35.6%)	
	More than 1 week	10(15.2%)	56(84.8%)	0.001
	More than 2 week	0 (0.0%)	09(100%)	
Posl n Ureler	Proximal	28(51.9%)	26(48.1%)	

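### Randomised patients were excluded with no breakdown by arm, and the counts do not reconcile (180, 182 and 179; 89/93 against 77/102), so the analysed arms cannot be verified

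*Combined protocol and SAP*

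**What the plan says.** - **Randomised.** The Abstract (Methodology) divides 208 patients into "104 patients in the Tamsulosin group and 104 patients in Silodosin group (1:1 ratio".
- **Excluded afterwards.** "16 patients were subsequently excluded on account of premature end of study, and 12 due to being lost to follow-up". No split by arm is given, and the label attached to the 16 is not defined.
- **Remaining.** "Out of remaining 180 patients 89 were of Tamsulosin and 93 were in Silodosin group".
- **Analysed.** The Results begin from another total: "In our study there are total 179 patients out of which 74 are females (41.3%) and 105 males (58.7"%). The Figure 1 text adds that "Of the patients, 43% were advised to take Tamsulosin" and gives 57% for silodosin.
- **Outcome.** The Operational Definitions set stone clearance as a yes/no finding on plain X-ray at 4 weeks. The Results tabulate time to removal in three bands, the last being 22-28 days. For that last period the Figure 2 text says "57 patients on Tamsulosin while 13 on Silodosin were able to eliminate stones".
- **Analysis rules.** The Data Analysis Procedure names the software, a t-test and a 0.05 threshold. It defines no analysis set and no rule for a missing 4-week outcome. The Sample Size section allows 10% for loss to follow-up.

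**The concern.** Removing patients after randomisation is safe only if removal is unrelated to arm and outcome. A reader can judge that only from a flow by arm with reasons. Here the breakdown is absent, and the totals that would let a reader infer it disagree with each other. The arm sizes behind every reported result (77 and 102) do not follow from the arm sizes the Abstract says remained (89 and 93).

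Two things are at stake. The first is whether the analysed arms are the randomised arms less some losses. The second is the 4-week result: if every analysed patient in both arms cleared, the analysed data show no difference on the defined endpoint, and the answer for all randomised patients turns on those left out. The Conclusion nonetheless says that silodosin expels stones more successfully and at a higher rate.

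**Working it through.** **1. The Abstract's own subtraction.** 208 - 16 - 12 = 180, as stated. But 89 + 93 = 182.

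**2. Arm sizes behind the results.** These are not printed as arm sizes; they come from the table columns.

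| Variable | Tamsulosin | Silodosin |
|---|---|---|
| BMI | 72+5 = 77 | 94+8 = 102 |
| Laterality | 65+12 = 77 | 52+50 = 102 |
| Symptoms to CT | 67+10+0 = 77 | 37+56+9 = 102 |
| Position | 28+8+41 = 77 | 26+38+38 = 102 |
| Water intake | 59+18 = 77 | 49+53 = 102 |
| Analgesic | 26+51 = 77 | 16+86 = 102 |
| Removal time | 6+14+57 = 77 | 52+37+13 = 102 |
| Side effects | 61+9+2+5 = 77 | 91+6+1+4 = 102 |

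77 + 102 = 179; 77/179 = 43.0% and 102/179 = 57.0%, matching the Figure 1 text. The Abstract's split would give 89/182 = 48.9% tamsulosin.

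**3. Losses implied from 104/104** (two-sided Fisher's exact test).

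| Counts used | Tamsulosin lost | Silodosin lost | Total | p |
|---|---|---|---|---|
| 89/93 | 104-89 = 15 (14.4%) | 104-93 = 11 (10.6%) | 26 | 0.53 |
| 77/102 | 104-77 = 27 (26.0%) | 104-102 = 2 (1.9%) | 29 | 3e-7 |

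The stated number of exclusions is 28, and neither row gives it. From 89/93 to 77/102, tamsulosin falls by 12 and silodosin rises by 102 - 93 = 9.

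**4. Four-week clearance.** Inputs: 77/102 analysed, all cleared by day 28 as the removal-time table prints, and 104 randomised per arm. Difference = silodosin minus tamsulosin.

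| Treatment of the missing (27 and 2) | Tamsulosin | Silodosin | Difference |
|---|---|---|---|
| Left out | 77/77 | 102/102 | 0 |
| All not cleared | 77/104 = 74.0% | 102/104 = 98.1% | +24.0 points (95% CI 15.2 to 32.9; p = 3e-7) |
| All cleared | 104/104 | 104/104 | 0 |
| Extreme against silodosin | 104/104 | 102/104 = 98.1% | -1.9 points (p = 0.50) |
| Extreme for silodosin | 77/104 = 74.0% | 104/104 | +26.0 points |

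The interval is Wald: d ± 1.96 × √(p₁q₁/104 + p₂q₂/104).

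If 89/93 were the retained counts, all cleared, with missing counted as not cleared: 89/104 = 85.6% v 93/104 = 89.4%, or +3.8 points (95% CI -5.1 to 12.8; p = 0.53). The choice between the two sets of counts therefore moves the missing-as-failure result from +3.8 to +24.0 points.

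**5. If the last band hides uncleared patients.** The removal-time table has no row for stones not expelled. If nobody in the 22-28 day band had cleared, the analysed figures would be (6+14)/77 = 26.0% v (52+37)/102 = 87.3%. The bounds in step 4 would not then apply.

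**6. Removal in under 14 days**, from the table's counts: 6/77 v 52/102. Crediting all 27 missing tamsulosin patients and neither missing silodosin patient gives (6+27)/104 = 31.7% v 52/104 = 50.0%, p = 0.011.

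**7. Power.** At 64% v 83% (two-sided 5%, no continuity correction) power is 87.9% with 104/104, 83.4% with 89/93 and 82.4% with 77/102. The planned effect remains detectable, so the problem is not power.

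**The case against.** **Attrition alone could explain part of this.** 104/104 and 89/93 are successive stages and can both be true; 15 v 11 losses are unremarkable. This stands. The contradictions are 180 against 182 against 179, and 89/93 against 77/102.

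**The Abstract may simply be wrong.** A counting or typing error there would leave the Results intact. This is possible, but 77/102 would then be the true flow, and its 27 v 2 losses would need explaining more than 15 v 11 would.

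**Strongly differential dropout is not established.** A reader might infer it from 26.0% v 1.9%. That comparison holds only if 77/102 is right, and the 29 losses it implies do not match the stated 28.

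**Movement of patients between arms is not established.** A reader might infer it from the nine extra silodosin patients. It is not needed: on the Abstract's figures 11 silodosin patients had been excluded, and reinstating nine gives 102, still below 104. An Abstract error, reinstated exclusions and arm misclassification all fit, and the documents do not say which applies.

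**Selective removal of treatment failures is not established.** The term used for the 16 could mean that the trial closed early or that the patient stopped early. Only the second would suggest it, and the text does not decide.

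**The 100% clearance may be an artefact.** With no row for stones not expelled, uncleared patients may have been placed in the last band. The Figure 2 text, which describes the 57 and 13 as having eliminated their stones, points the other way. The matter needs a check against the records.

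**The early contrast is robust.** The difference in removal before 14 days survives the worst case in step 6. This stands if membership of the 77 and 102 is trusted, which is what the count conflict leaves open.

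**Conclusion.** The concern holds. The patient counts are inconsistent as written, 28 randomised patients by the Abstract's own count were excluded with no split by arm, and no analysis set or missing-outcome rule is given. The analysed arms therefore cannot be verified as the randomised arms less known losses.

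The size depends on two assumptions: that 77/102 is the true analysed split, and that the removal-time table is right in showing everyone cleared by day 28. With both, the analysed data show no 4-week difference, and the all-randomised result runs from -1.9 to +26.0 points. The claim of a higher expulsion rate is then unsupported on the defined endpoint until the missing outcomes are dealt with. If the second assumption fails, the 4-week rates must be recomputed before any bound is meaningful. The under-14-day advantage survives if the first assumption holds.

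The documents do not support a firm statement that dropout differed by arm, that patients changed arm, or that failures were removed. This should be fixed before the results are relied on.

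**What to change.** 1. Reconcile the flow by arm against the allocation list, giving the number, reason and timing of every exclusion and saying what the label for the 16 means. Correct 180/182/179 and 89/93 against 77/102 wherever they appear.
2. Analyse every randomised patient in the arm allotted. For 4-week clearance, make missing counted as not cleared the main display, with best- and worst-case bounds beside it. Confirm from records whether any analysed patient was uncleared at 4 weeks, and add a row for stones not expelled to the removal-time table.
3. In the time-to-expulsion analysis, include the excluded patients, censored at last contact where that date is recorded, and state how many lack one.
4. Limit the Abstract and Conclusion to what survives steps 1-3.

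Cost: re-tabulation, plus retrieval of last-contact dates and 4-week findings. The documents show only three time bands and one scheduled visit, so some dates may not exist. The reported rates may become less favourable.
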